10.4. Appendix 4: Derived and Transformed Data

10.4.1. General

Multiple Measurements at One Analysis Time Point

 • Mean of the measurements will be calculated and used in any derivation of summary statistics but if listed, all data will be presented. • If there are two values within a time window the value closest to the target day for that window will be used. If values are the same distance from the target then the mean will be taken. • Participants having both High and Low values for Normal Ranges at any post-baseline visits for safety parameters will be counted in both the High and Low categories of “Any visit post-baseline” row of related summary tables. This will also be applicable to relevant Potential Clinical Importance summary tables.
Study Day

 • Calculated as the number of days from date of study drug administration (Dose Date): 
 • Ref Date = Missing → Study Day = Missing • Ref Date < Dose Date → Study Day = Ref Date – Dose Date • Ref Date ≥ Dose Date → Study Day = Ref Date – (Dose Date) + 1

10.4.2. Study Population

Demographics
Age

 • GSK standard IDSL algorithms will be used for calculating age where birth date will be imputed as follows: 
 ○ Only the year of birth will be collected. The date and month will be imputed as PPD • Birth date will be presented in listings as ‘YYYY’.
Body Mass Index (BMI)

 • Calculated as Weight (kg) / [Height (m)²]

10.4.3. Safety

ECG Parameters
RR Interval

 • IF RR interval (msec) is not provided directly, then RR can be derived as: 
 [1] If QTcB is machine read & QTcF is not provided, then: $RR = \left[\left(\frac{QT}{QTcB} \right)^2 \right] * 1000$ [2] If QTcF is machine read and QTcB is not provided, then: $RR = \left[\left(\frac{QT}{QTcF} \right)^3 \right] * 1000$ • If ECGs are manually read, the RR value preceding the measurement QT interval should be a collected value THEN do not derive.

ECG Parameters

- Machine read values of RR should not be replaced with derived values.

Corrected QT Intervals

- When not entered directly in the eCRF, corrected QT intervals by Bazett's (QTcB) and Fredericia's (QTcF) formulas will be calculated, in msec, depending on the availability of other measurements.
- IF RR interval (msec) is provided then missing QTcB and/or QTcF will be derived as:

$$QT_{cB} = \frac{QT}{\sqrt{\frac{RR}{1000}}}$$

$$QT_{cF} = \frac{QT}{\sqrt[3]{\frac{RR}{1000}}}$$

10.5. Appendix 5: Reporting Standards for Missing Data

10.5.1. Premature Withdrawals

Element	Reporting Detail
General	
 • Participant study completion (i.e. as specified in the protocol) was defined as completing all phases of the study including the follow-up visit. • Withdrawn participants may be replaced in the study. • All available data from participants who were withdrawn from the study will be listed and all available planned data will be included in summary tables and figures, unless otherwise specified. • Early termination visits will be summarized as early termination visits.

10.5.2. Handling of Missing Data

Element	Reporting Detail
General	
 • Missing data occurs when any requested data is not provided, leading to blank fields on the collection instrument: 
 ○ These data will be indicated by the use of a “blank” in participant listing displays. Unless all data for a specific visit are missing in which case the data is excluded from the table. ○ Answers such as “Not applicable” and “Not evaluable” are not considered to be missing data and should be displayed as such.
Outliers	
 • Any participants excluded from the summaries and/or statistical analyses will be documented along with the reason for exclusion in the clinical study report.

10.5.2.1. Handling of Missing and Partial Dates

Element	Reporting Detail
General	
 • Partial dates will be displayed as captured in subject listing displays.
Adverse Events	
 • The eCRF allows for the possibility of partial dates (i.e., only month and year) to be recorded for AE start and end dates; that is, the day of the month may be missing. In such a case, the following conventions will be applied for calculating the time to onset and the duration of the event: 
 ○ Missing Start Day: First of the month will be used unless this is before the date of study treatment; in this case the study treatment date will be used and hence the event is considered Treatment Emergent as per Appendix 2: Study Phases and Treatment Emergent Adverse Events. ○ Missing Stop Day: Last day of the month will be used, unless this is more than 2 days after the date of study treatment; in this case the study treatment date will be used. • Completely missing start or end dates will remain missing, with no imputation applied. Consequently, time to onset and duration of such events will be missing.
Concomitant Medications/ Medical History	
 • Partial dates for any concomitant medications recorded in the CRF will be imputed using the following convention: 
 ○ If the partial date is a start date, a '01' will be used for the day and 'Jan' will be used for the month ○ If the partial date is a stop date, a '28/29/30/31' will be used for the day (dependent on the month and year) and 'Dec' will be used for the month. • The recorded partial date will be displayed in listings.

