9.2.1. Time Period and Frequency for Collecting AE and SAE Information

- All SAEs will be collected from the signing of the ICF until the Follow-Up Visit at the time points specified in the SoA (Section 2).
- All AEs will be collected from the start of treatment until the Follow-Up Visit at the time points specified in the SoA (Section 2).
- Medical occurrences that begin before the start of study treatment but after obtaining informed consent will be recorded on the Medical History/Current Medical Conditions section of the electronic case report form (eCRF) not the AE section.
- All SAEs will be recorded and reported to the sponsor or designee immediately and under no circumstance should this exceed 24 hours, as indicated in [Appendix 7](#). The investigator will submit any updated SAE data to the sponsor within 24 hours of it being available.
- Investigators are not obligated to actively seek AEs or SAEs in former study participants. However, if the investigator learns of any SAE, including a death, at any time after a participant has been discharged from the study, and he/she considers the event to be reasonably related to the study treatment or study participation, the investigator must promptly notify the sponsor.
- The method of recording, evaluating, and assessing causality of AEs and SAEs and the procedures for completing and transmitting SAE reports are provided in [Appendix 7](#).

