10.2. Appendix 2: Study Phases and Treatment Emergent Adverse Events

10.2.1. Study Phases

For Groups A, B, C, D, and E, assessments and events will be classified according to time of occurrence relative to the date/time of the study treatment.

Study Phase	Definition
Pre-Treatment	Date/Time < Study Treatment Date/Time
On-Treatment	Study Treatment Date/Time ≤ Date/Time ≤ Study Treatment Date/Time + 2 Days
Post-Treatment	Date/Time > Study Treatment Date/Time + 2 Days

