10.2.2. Treatment Emergent Flag for Adverse Events

Flag	Definition
Treatment Emergent	
 If AE onset date/time is on or after treatment date/time & on or before the treatment stop date/time with 2 days lag time. Study Treatment Date/Time ≤ AE Start Date/Time ≤ Study Treatment Date/Time + 2 days.

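### The SAP's missing-start-day rule moves an adverse event recorded in a month wholly before dosing to the dosing date and flags it treatment-emergent

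*SAP*

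**What the plan says.** SAP 10.5.2.1 covers AE dates recorded with month and year but no day. When the day of onset is unknown, the rule reads: "First of the month will be used unless this is before the date of study treatment; in this case the study treatment date" is used instead, with the stated result "hence the event is considered Treatment Emergent as per Appendix 2". For a missing stop day, the last day of the month is used unless it is more than 2 days after dosing, when the dosing date is used. The section says these conventions serve to calculate time to onset and duration, and that listings show partial dates as they were recorded.

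SAP 10.2.2 defines the treatment-emergent window as "Study Treatment Date/Time ≤ AE Start Date/Time ≤ Study Treatment Date/Time + 2 days". SAP 10.2.1 defines the Pre-Treatment phase as "Date/Time < Study Treatment Date/Time".

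Protocol 9.2.1 sets different collection periods: "All SAEs will be collected from the signing of the ICF until the Follow-Up Visit", but "All AEs will be collected from the start of treatment until the Follow-Up Visit". It sends other medical occurrences between consent and dosing to the medical history pages. Protocol Section 2 allows Screening up to 30 days before Day -1 and schedules AE/SAE review at Screening and Check-in.

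**The concern.** Moving a partial onset date to the dosing date is a sensible caution when the event is in the dosing month, because the missing day then decides whether onset was before or after dosing. When the recorded month is earlier, the missing day decides nothing: every day of that month precedes dosing. The rule still moves the event, so it overrides information already recorded.

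At stake are the treatment-emergent flag, the study phase, time to onset and duration for a pre-dose SAE in a participant who is then dosed, and any display that uses those variables. The classification would also depend on how completely the date was recorded: with a full date the event is Pre-Treatment, and without the day it is treatment-emergent.

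**Working it through.** The plan gives no figure for this rule, so there is none to reproduce. The check applies the rule as written.

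**Inputs.** Start and stop rules: SAP 10.5.2.1. Flag and phase definitions: SAP 10.2.2 and 10.2.1. Study day: SAP 10.4.1. SAE collection from consent: Protocol 9.2.1. Screening up to 30 days before Day -1, hence up to 31 days before Day 1: Protocol Section 2. Assumed here: an example dosing date of 16 July 2018; dosing equally likely on each of 365 days (1 March 2018 to 28 February 2019); onset uniform over the pre-dose window.

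**1. The rule as a formula.** Let D be the dosing date and F the first of the recorded month. Imputed start = D if F < D, otherwise F. If the recorded month is before the dosing month, F < D always holds, so start = D. Since D ≤ D ≤ D + 2 days, the event is flagged.

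**2. Example, D = 16 July 2018.**

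| Recorded start | F | Imputed start | Flag | What the record shows |
|---|---|---|---|---|
| June 2018 | 1 June | 16 July | Treatment-emergent | Every day in June precedes dosing |
| July 2018 | 1 July | 16 July | Treatment-emergent | Undetermined; cautious default |
| August 2018 | 1 August | 1 August | Not treatment-emergent | After the 2-day window |

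Only the June row is wrong. The same SAE fully dated 20 June is before 16 July and so is Pre-Treatment under SAP 10.2.1.

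**3. Time to onset and duration.** The imputed study day is 16 July − 16 July + 1 = 1. With a 31-day window the true June onset lies between 15 June (study day −31) and 30 June (study day −16). If the stop is also recorded as June, it is imputed to 30 June, and duration = 30 June − 16 July + 1 = −15 days.

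**4. Can such records exist?** Yes, for SAEs. They are collected from consent and reviewed at Screening and Check-in. The protocol's sentence sending pre-dose occurrences to medical history does not name SAEs as an exception, but the same section requires SAEs from consent. Non-serious pre-dose events are not recorded as AEs, so the problem is confined to SAEs.

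**5. Share of pre-dose onsets in an earlier month.** An onset k days before dosing is in an earlier month when the dosing day of the month is k or less. That gives k dosing days per month, or 12k per year. For a window of w days:

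share = 12 × w(w + 1)/2 ÷ (365w) = 6(w + 1)/365

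- w = 7: 48/365 = 13%
- w = 14: 90/365 = 25%
- w = 31: 12 × 496 = 5,952 of 365 × 31 = 11,315. Months shorter than k remove 10 (6 for February, 1 for each of four 30-day months), leaving 5,942 of 11,315 = 52.5%. Direct enumeration gives the same count.

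The rule as written flags all 5,942. With the substitution limited to the dosing month, it flags 0 of 5,942, and dosing-month onsets stay treatment-emergent.

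**The case against.** The strongest reply concerns consequence. Tables 2.1 to 2.4 in SAP Appendix 8 are titled for all, drug-related, common non-serious and serious AEs; none is titled or annotated as restricted to treatment-emergent events. On those titles a pre-dose SAE in a dosed participant is counted in Table 2.4 whatever its flag. No planned table summarises time to onset or duration. The SAE listing (Listing 18) would show the recorded month. All of this stands.

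The trigger is also narrow. It needs an SAE between consent and dosing, an unknown day although SAEs are reportable within 24 hours, a recorded month before the dosing month, and a participant who is dosed anyway. Hepatically impaired participants must stay clinically stable through Screening (inclusion 3), related conditions must have been stable for a month before dosing (exclusion 1), and eligibility is rechecked at Check-in. Many participants with a screening SAE would never enter the Safety population. This stands too.

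A reader might infer that one misdated SAE adds 12.5 percentage points (1/8) to a group of 8, or 16.7 (1/6) to a group of 6, and that the impaired groups would carry most of the error. The documents support neither. No planned percentage is defined on the flag, and no rate of screening SAEs by hepatic group is given, while the stability criteria work against the second inference.

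None of this makes the rule right. The SAP itself states the treatment-emergent result, and for an earlier month that result conflicts with its own phase definition.

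**Conclusion.** The rule is wrong as written for events recorded in a month before dosing. It assigns a treatment-emergent flag and a dosing-date onset to an event that the record shows began earlier, and it can produce a negative duration. The effect is limited to the flag, study phase, time to onset, duration and any display using them. No change in a planned table percentage is shown, and the recorded date remains visible in listings.

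The case should be rare. If pre-dose SAEs with a missing day did occur, the share provably misclassified would be about 13% for a 7-day pre-dose window, 25% for 14 days and at most 53% for the full 31 days. These shares rest on uniform onset and dosing dates and a single screening window; the documents give no actual distribution. The priority is low, but the correction is simple and worth making.

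**What to change.** Replace the missing-start-day sentence in SAP 10.5.2.1 with:

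> *If the recorded month and year equal those of study treatment and the first of the month is before the treatment date, use the study treatment date. Otherwise use the first of the recorded month; events in an earlier month are Pre-Treatment and not treatment-emergent.*

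In the example, a June start becomes 1 June 2018 and is not treatment-emergent, while a July start still becomes 16 July and is. The first of the month is preferable to the last day for earlier months: with a start recorded as June and a complete stop date of 12 June, a last-day rule would put onset on 30 June, after the stop. The imputed first of the month may precede consent, so time to onset remains approximate, but the classification is correct.

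The cost is one SAP sentence and one condition in the AE dataset program.

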9.2.3. Follow-up of AEs and SAEs

After the initial AE/SAE report, the investigator is required to proactively follow each participant at subsequent visits/contacts. All SAEs, and nonserious AEs of special interest (as defined in Section 3.3.1), will be followed until the event is resolved, stabilized, otherwise explained, or the participant is lost to follow-up (as defined in Section 8.3). Further information on follow-up procedures is given in [Appendix 7](#).

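### The SAP's rule for a missing AE stop day can place the stop before the onset, because it has no floor at onset

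*SAP*

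**What the plan says.** SAP 10.5.2.1 (Handling of Missing and Partial Dates, Adverse Events row) notes that the eCRF accepts AE start and end dates without the day. It then says that "the following conventions will be applied for calculating the time to onset and the duration of the event". Two rules follow.

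- **Start day not recorded.** "First of the month will be used unless this is before the date of study treatment; in this case the study treatment date" is used instead.
- **Missing stop day.** Month-end is used, "unless this is more than 2 days after the date of study treatment; in this case the study treatment date will be used".

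Neither rule requires the stop to be on or after the onset, and no other section adds that condition. The General row of the same table says "Partial dates will be displayed as captured in subject listing displays", so listings show the date as recorded.

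Onsets after the dosing day are within scope. Protocol 9.2.1 states: "All AEs will be collected from the start of treatment until the Follow-Up Visit". The Synopsis puts that visit about 10 days (±5) after dosing.

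**The concern.** The stop-day rule refers to only one date, the dosing date. Once month-end is more than 2 days past dosing, the stop goes back to the day of dosing, whenever the event began. Any AE known to have started on a later day then ends before it starts.

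The SAP gives duration as a purpose of these conventions, so following the text literally produces impossible values for a variable it says will be derived. A programmer who noticed would have to depart from the plan without authority in the text. A programmer who did not would carry zero or negative durations into the AE analysis data.

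**Working it through.** The documents give no figure on this point, so there is none to reproduce. The check applies the rule as written.

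**Inputs.** D = dosing date; L = last day of the recorded stop month. Imputed stop = D if L − D > 2 days, otherwise L (SAP 10.5.2.1). The AE window is D to D + 10, with 5 and 15 as the extremes (Protocol Synopsis).

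**Algebra.** If the reset applies and the known onset is D + k, then stop − onset = D − (D + k) = −k. This is negative for every k ≥ 1 and needs no assumption. Onset on the dosing day gives 0 and no conflict. Without the reset, the stop is month-end, which cannot precede an onset in or before that month.

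**Example.** Dosed 10 June, onset 12 June, stop recorded as June. L = 30 June, which is 20 days after dosing, so the reset applies and the stop becomes 10 June. Stop − start = −2. The SAP states no AE duration formula. With the +1 convention that it uses elsewhere ("Study Day = Ref Date – (Dose Date) + 1"), the result is −1. Under that convention an onset one day after dosing gives 0.

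**When the reset applies.** For a stop in the dosing month, only the last three dosing days of each month escape: 365 − 12 × 3 = 329 of 365 dosing dates, or 90%. For a stop in a later month it always applies (4,620 of 4,620 cases with onset after the dosing day, 10-day window). The imputed date then also contradicts the recorded month: dosed 28 June, stop recorded as July, imputed stop 28 June.

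**Enumeration.** All 365 dosing dates were crossed with every known onset after the dosing day and every stop on or after that onset, equally weighted. This counts cases; it does not forecast rates. For the 10-day window there are 10 + 9 + … + 1 = 55 onset/stop pairs, and 365 × 55 = 20,075.

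| Window (days) | Cases | Stop before onset | Of these, 0 under stop − start + 1 | Of these, negative under stop − start + 1 |
|---|---|---|---|---|
| 5 | 5,475 | 5,427 | 1,789 | 3,638 |
| 10 | 20,075 | 20,027 | 3,614 | 16,413 |
| 15 | 43,800 | 43,752 | 5,439 | 38,313 |

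Under stop − start, every case in the third column is negative. The 48 cases without conflict in each row are those where no reset applies. Adding dosing-day onsets to the 10-day window gives 20,027 of 24,090 (83%).

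**Start day also missing (10-day window).** A dosing-month start is itself set to the dosing date, so with the reset the duration is 0 or 1; none of 21,450 cases is negative. A later-month start is set to the first of that month, and the reset stop precedes it in 2,640 of 2,640 cases.

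**Mean error in the stop date (all onsets, equal weights).**

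| Rule | 5 days | 10 days | 15 days |
|---|---|---|---|
| As written | −3.3 | −6.7 | −10.0 |
| As written, with floor at onset | −1.7 | −3.3 | −5.0 |
| Month-end capped at end of window, with floor | +1.6 | +3.0 | +4.3 |

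Neither alternative ever puts the stop before onset.

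**The case against.** The best counter-argument is that nothing reported depends on this value. Safety Tables 2.1 to 2.12 (SAP 10.8.5) include no summary of AE duration, and no listing title names it. The treatment-emergent flag is set from onset alone ("If AE onset date/time is on or after treatment date/time"). Whether a derived duration appears in the AE listings depends on display shells that are not in the documents. All of this stands, and it keeps the point minor.

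The counts could also be misread as rates. They give a late onset or a long event the same weight as a dosing-day event. Participants stay in the clinic from Day −1 to Day 3 (Protocol Table 1), so an event that starts and ends there is unlikely to lack a stop day. That is fair: the documents support no frequency. The sign of the result, however, comes from the algebra and not from the weights.

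A third argument is that AE analyses follow the sponsor's core data standards (SAP 8.1), which may handle this case. Those standards are not available here, and SAP 10.5.2.1 states its own explicit rule, so they do not rescue the text.

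Finally, choosing between month-end and the reset is partly a preference: with a 10-day window, one errs by +3.0 days and the other, with a floor, by −3.3. That is right, and only the floor is a correction.

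**Conclusion.** The concern holds, as a minor point. Whenever the reset applies and onset is known to be after the dosing day, the imputed stop precedes onset, by as many days as onset follows dosing. The same happens when both days are missing and the start is in a month after dosing.

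The conclusion rests only on the rule's wording and on reading the month in it as the recorded stop month. The percentages rest on an equal-weight calendar and are conditional on a missing stop day, whose frequency is not given. For scale only, an assumed 20 to 60 AEs with 2% to 10% missing a stop day gives at most 20 × 0.02 = 0.4 to 60 × 0.10 = 6 affected events. The treatment-emergent flag, planned safety tables, PK results and endpoints are unchanged.

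**What to change.** Add one sentence to the missing-stop-day rule in SAP 10.5.2.1: *the imputed stop date will not be earlier than the recorded or imputed AE onset date.* This alone removes every impossible value, for one sentence of text and one line of programming. Durations would still be understated on average (−3.3 days with a 10-day window, against −6.7 now), and a later-month stop could still be imputed into an earlier month than the one recorded.

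Optionally, replace the reset as well: *last day of the recorded month, capped at the Follow-up Visit or study end date (last contact if the AE is followed beyond the visit), and never earlier than the recorded or imputed onset.* The allowance for last contact is needed because Protocol 9.2.3 says SAEs and AEs of special interest "will be followed until the event is resolved, stabilized, otherwise explained, or the participant is lost to follow-up". This version overstates duration on average (+3.0 days with a 10-day cap) and needs a cap date for each participant, so it takes slightly more programming. It would also be worth stating the AE duration formula in the same place.
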